### Demographics and Baseline Characteristics

standardized to obtain a continuous single unit prior ESA dose in terms of epoetin IV (IU/week). The standardization will be carried with the following formula based on literature review:

- For subjects taking epoetin IV
  - Standardized mean prior ESA dose (IU/week) = epoetin IV dose (IU/week)
- For subjects taking epoetin SC
  - Standardized mean prior ESA dose (IU/week) = (161/113)\*epoetin SC dose(IU/week): [Besarab. 2002]
- For subjects taking darbepoetin alfa IV or SC
  - Standardized mean prior ESA dose (IU/week) = 250\*darbepoetin alfa dose (µg/week)
- For subjects taking epoetin beta pegol IV or SC
  - Standardized mean prior ESA dose (IU/week) = 208\*epoetin beta pegol dose (µg/week)
- Prior ESA dose will be calculated using a weighted mean:
  - Mean prior ESA dose (µg/week or IU/week) =  $([dose\_w]_1 * [duration]_1 + \dots + [dose\_w]_n * [duration]_n) / ([duration]_1 + \dots + [duration]_n)$   
 where
    - $[Dose\_w]_n = [dose]_n * [frequency]_n$
    - $[Duration]_n = [Prior\ ESA\ start\ date]_{n+1} - [prior\ ESA\ start\ date]_n^*$   
 or  
 $[Randomization\ date] - [prior\ ESA\ start\ date]_n^*$   
 when  $n^{th}$  record is the last prior ESA dose

\*Using "[end date] – [start date] + 1" may be inappropriate because the start date may be identical with the end date in case the dose frequency is once daily or twice daily, etc.

Note: Frequency is defined as follows:

If subject receives prior ESA x times per week → frequency = x

If subject receives prior ESA every x weeks → frequency = 1/x

If subject receives prior ESA x times per month → frequency = x \* 7 / 30.4375

If subject receives prior ESA x times per day → frequency = x \* 7/duration

once daily (QD) = 1 time per day, twice daily (BID) = 2 times per day, etc...

- Prior ESA dose during the period of 12 weeks prior to randomization will be used for calculation.
- To obtain this, some records may be converted for calculation because some dosing records may include both before and after the period or may not include the period.
  - If a start date of dosing is before 12 weeks prior to randomization (i.e., study day < -84), the start date will be replaced to the date of study day = -84 for the calculation.
  - This conversion makes the records before 12 weeks prior to randomization ignorable because the records will lose their information and weighting of duration before the period.

Demographics and Baseline Characteristics						

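### The 12-week cut-off for prior ESA dose fails for single doses coded per day: a record straddling Day −84 keeps its full dose, and a wholly earlier record has an undefined frequency

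*SAP*

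**What the plan says.** SAP 15.6.2, under Prior ESA Dose (IU/week) at Baseline, gives these rules:

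- **Mean.** "Prior ESA dose will be calculated using a weighted mean": the sum of weekly dose × duration, divided by the sum of durations. Weekly dose is dose × frequency.
- **Duration.** The next record's start date minus this record's start date; for the last record, the randomization date minus its start date. End dates are avoided "because the start date may be identical with the end date in case the dose frequency is once daily or twice daily".
- **Frequency, per-day records.** "If subject receives prior ESA x times per day → frequency = x \* 7/duration".
- **Frequency, other records.** These do not involve duration, for example "If subject receives prior ESA every x weeks → frequency = 1/x".
- **Window.** Only the 12 weeks before randomization count. If a start date lies before study day −84, "the start date will be replaced to the date of study day = -84 for the calculation".
- **Claimed effect.** "This conversion makes the records before 12 weeks prior to randomization ignorable", on the ground that such records lose both their information and their weight.

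Three of the four records in the SAP's illustration are single epoetin administrations coded once daily. The resulting dose feeds the prior ESA dose bands (cuts at 4,500 and 6,000 IU/week) and the ERI tertiles of SAP 5.4.2.

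**The concern.** Only one duration is defined, and the converted start date is to be used in the calculation. The converted duration therefore enters both the weight and, for per-day records, the frequency. The two cancel, so truncation cannot remove a dose given before the window, which is what the SAP says it does.

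At stake is the classification of subjects by prior ESA dose and ERI. These variables define subgroups for the MMRM (SAP 7.1.5.1) and the logistic model (SAP 7.2.5.1). They also define the Hgb and dose summaries of SAP 7.3.2, and prior ESA dose is an axis of the scatter plots of SAP 7.4.2.

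**Working it through.** **1. Reproduce the SAP's figure.** The illustration has weekly doses 2625, 2625, 3500 and 2250 IU over 2, 2, 3 and 9 days:

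(2625×2 + 2625×2 + 3500×3 + 2250×9) / 16 = 41250 / 16 = 2578.1 IU/week.

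This agrees. The records span only 16 days, so the illustration never tests the Day −84 rule.

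**2. Cancellation.** For a per-day record, weekly dose × duration = (dose × 7x / duration) × duration = 7x × dose, whatever the duration. Moving the start to Day −84 changes only the denominator.

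**3. Wholly earlier record.** If the next record also starts on or before Day −84, both starts become Day −84 at the latest. The duration is then 0 and the frequency is 7x/0. This is undefined, not an inflation; the result depends on the code.

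**4. Records where the rule works.** An every-4-weeks record of 100 µg starting on Day −200 is cut to 84 days at 25 µg/week. With the SAP's factor of 208 that is 5,200 IU/week, as intended.

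**5. Size of the inflation.** Assume equal single doses, each its own once-daily record, with n doses inside the window and one straddling record that has a fraction p of its interval inside. Three values can be compared:

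- as written: (n + 1) × 7 × dose / 84
- prorated (weekly dose from the unconverted interval, weight clipped): (n + p) × 7 × dose / 84
- doses inside the window only: n × 7 × dose / 84

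The ratios are (n + 1)/(n + p) against prorated and (n + 1)/n against window-only. The regimens and dates are assumptions, since the documents contain no patient records.

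| Regimen | n | p | As written (IU/week) | Prorated | Window-only | Excess vs prorated | Excess vs window-only |
|---|---|---|---|---|---|---|---|
| Epoetin 1500 IU three times weekly, 3-day gap straddling | 36 | 2/3 | 4,625 | 4,583 | 4,500 | 0.9% | 2.8% |
| Darbepoetin alfa 20 µg weekly (×250) | 12 | 6/7 to 1/7 | 5,417 | 5,357 to 5,060 | 5,000 | 1.1% to 7.1% | 8.3% |
| Epoetin beta pegol 100 µg four-weekly (×208) | 3 | 27/28 to 1/28 | 6,933 | 6,871 to 5,262 | 5,200 | 0.9% to 31.8% | 33.3% |

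For the epoetin row with p = 1/3, the excess against prorated is 37/36.33 − 1 = 1.8%.

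**6. Band crossing.** In the four-weekly case 6,933 lies above the 6,000 cut. The prorated value lies below it when (25c + 2100)/84 × 208 < 6,000, where c is the number of days of the straddling interval inside the window. That gives c ≤ 12, that is, a last dose 16 to 27 days before Day 1. For 75 µg all values scale by 0.75: 5,200 as written against 3,900 window-only, crossing 4,500 under the same condition on c.

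**7. No straddle.** With doses exactly on Days −84, −56 and −28 nothing is moved: 3 × 700 / 84 = 25 µg/week, which is correct.

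**The case against.** The algebra is hard to dispute, but four points limit it.

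- **Coding.** The SAP has an every-x-weeks category for long-interval ESAs, and such records are unaffected. Its only per-day examples are epoetin records 2 to 3 days apart. A reader might infer that errors near one third are to be expected; nothing in the documents shows four-weekly drug entered as single once-daily records. This stands.
- **Scheduling.** Protocol 4.2 asks that Day 1 fall as close as possible to the next scheduled ESA dose, which often puts a regular dose on or near Day −84. Four-weekly doses on Days −85, −57 and −29 also give exactly 25 µg/week as written (3 × 700 / 84). This reduces how often inflation arises. It does not rescue wholly earlier per-day records, whose frequency stays undefined. Records that old are plausible: Protocol 5.1 requires one ESA for at least 10 weeks before screening, and screening adds 2 to 4 weeks.
- **Zero-length records.** A reader might infer that these also inflate the mean. As written they do not; they are undefined. Dropping them matches the SAP's stated intent, but the formula does not say so.
- **Consequence.** A reader might infer that the main efficacy conclusions are at risk. SAP 5.4.1 uses prior ESA dose and ERI neither as strata nor as covariates. SAP 7.2.5.1 calls its subgroup analyses exploratory, and ERI is split by tertile, so only rank changes matter. The inputs precede randomization, so misclassification is independent of the assigned arm.

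It can also be said that a programmer might take frequency from the unconverted duration. That would avoid the problem, but the SAP does not instruct it.

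**Conclusion.** The statement that truncation makes earlier records ignorable is wrong for per-day records and right for all other codings. At most one straddling record per subject inflates the mean, and there is no inflation when a dose falls exactly on Day −84. Against a prorated mean the excess is about 1 to 2% for thrice-weekly epoetin and 1 to 7% for weekly darbepoetin alfa (about 3% and 8% against window-only doses). The four-weekly range of about 1 to 32% (33% window-only), with possible crossing of the 4,500 or 6,000 cut, is conditional on a coding that the documents do not show. How many subjects have per-day records near Day −84 is unknown.

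ERI carries the same percentage error, because it is this dose divided by dry weight and Day 1 Hgb. The effect is confined to prior ESA dose, ERI, and the subgroup analyses, summaries and plots built on them. The primary and principal secondary tests are unaffected. This is a minor correction, worth making because the text does not do what it says.

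**What to change.** In SAP 15.6.2, for records coded x times per day:

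1. Compute the weekly dose from the unconverted interval to the next dose.
2. Clip only the weight (duration) to the 84-day window.
3. Exclude records whose clipped duration is 0.
4. State which interval gives the weekly dose of the last record, for example the preceding dosing interval, and what to do when there is none.

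Step 4 is needed because the last record, whose interval ends at randomization, has the same cancellation and steps 1 to 3 do not correct it. With 100 µg on Days −85, −57, −29 and −1, steps 1 to 3 give (25×27 + 700 + 700 + 700)/84 = 33.04 µg/week, barely below the 33.33 obtained as written. Using the preceding 28-day interval for the last record gives (25×27 + 700 + 700 + 25×1)/84 = 25 µg/week.

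The cost is a few lines of text and derivation code. The illustration and all records in the other frequency categories are unchanged. A small downside is that the result is a prorated mean, not the sum of doses given inside the window, and the SAP should say so.

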Registration with IWRS	X	X	X	X	X	X	X	X	X	X	X	X	X	
Study medication dispensing ^{2, 3}	X	X	X	X	X	X	X	X	X	X	X			
Study treatment compliance	X	X	X	X	X	X	X	X	X	X	X	X	X	
Vital signs (before and after dialysis) 4						X						X	X	X
Ophthalmology ⁵										-			\leftarrow	
ECG												X		
HemoCue Hgb	X	X	X	X	X	X	X	X	X	X	X	X		
Hematology		Hgb only		Hgb only		X		Hgb only		Hgb only		X	X	X
Clinical chemistry						X						X	X	X
Pregnancy test (serum hCG) 6						X						X	X	X
Estradiol, FSH ⁷														
PK 8														
Ferritin, TSAT						X						X	X	
Serum iron, TIBC, UIBC, serum transferrin, hepcidin						X						X	X	
iPTH												X		
HR-QoL												X	X	
Genetics sample 9														
AE assessment 10														—
Concomitant Medications Review	←													 

^{1.} Body weight is measured after dialysis. Both height and body weight are measured only at screening.

^{2.} Daprodustat/placebo will be dispensed once every 4 weeks, and darbepoetin alfa/placebo will be dispensed once every 2 weeks

^{3.} If a subject visit the study site only to receive study medication, only registration with the IWRS study medication dispensing, and study medication compliance will be required.

2015N266251_02 **CONFIDENTIAL** PHI201754

- 4. At visits without dialysis, only one measurement of each parameter will be obtained.
- 5. Ophthalmology exams should be conducted at the following time points.
 - Screening: anytime after consenting and prior to first dose of study medication (Day 1)
 - Week 12: window from weeks 10-14 (inclusive)
 - End of study: window from weeks 48-52 (inclusive)
 - Early study medication discontinuation: withdrawal eye exam as close to the last dose as possible (the repeat exams are not required if one has been performed within the 2 prior weeks).
- 6. Performed in females of childbearing potential.
- 7. Measured in female subjects only to determine the menopausal status (see Section 5.1.)
- 8. See Table 11.
- 9. Informed consent for optional Genetic research should be obtained before collecting a sample (see Section 7.6.).
- 10. See Section7.4.1.1..
- 11. The interval between screening and Day 1 should be 4 weeks in subjects treated with epoetin beta pegol every 4 weeks or darbepoetin alfa every 4 weeks in the prior ESA therapy.

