## 15. APPENDICES

### 15.1. Appendix 1: Protocol Deviation Management and Definitions for Per Protocol Population

#### 15.1.1. Exclusions from Per Protocol Population

A subject meeting any of the following criteria will be excluded from the Per Protocol population:

Number	Exclusion Description
01	Informed Consent in Deviation Category
02	Eligibility Criteria Not Met in Deviation Category
03	Not Withdrawn After Developing Withdrawal Criteria in Deviation Category
04	Wrong study treatment or assignment administered in Deviation Subcategory
05	Randomization procedures (e.g. subject randomized out of order) in Deviation Subcategory
06	Less than 3 out of 4 scheduled evaluable Hgb values from the primary efficacy evaluation period 
07	Subject received prohibited medication for more than 14 days during study period 
08	Non-compliance with randomized medication (compliance category of under compliant or over compliant)  during the primary efficacy evaluation period, based on eCRF randomized medication exposure and compliance forms

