
 
• Treatment compliance will be calculated for daprodustat as follows: 
 
○ Compliance (%) = [(Total # of tablets actual taken) / (Total # of tablets planned taken)] * 100 where Total # of tablets actual taken = Sum of (Numbers of Tablets Taken at Each Visit) Total # of tablets planned taken = Sum of [(Treatment Stop Date – Treatment Start Date + 1 day) x Planned # of tablet / day in Each Visit]
 
○ Daprodustat compliance will also be categorized based on calculated compliance: Calculated compliance < 80% → Under Compliant Calculated compliance ≥ 80% and ≤ 120% → Compliant Calculated compliance > 120% → Over Compliant
 
 
 
 
Where a container number is available, planned # of tablet/day is defined as follows according to the protocol:
 
 
○ 0 mg → 1 tablet/day (i.e., subjects takes placebo tablets)
 
○ 1 mg → 1 tablet/day
 
○ 2 mg → 1 tablet/day
 
○ 4 mg → 1 tablet/day
 
○ 6 mg → 1 tablet/day
 
○ 8 mg → 2 tablets/day
 
○ 12 mg → 2 tablets/day
 
○ 18 mg → 3 tablets/day
 
○ 24 mg → 4 tablets/day
 
 
where dose record is derived from prescribed dose.
 
Where a container number is not available (i.e., bottles not delivered to a subject), planned # of tablet/day will be 0 so that the treatment compliance will not be calculated.

Exposure
Where unscheduled (additional) bottles are being captured, the total # of tablets actual taken will be slotted to the corresponding scheduled visit.
Treatment Compliance of Darbepoetin Alfa

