
 
• Treatment compliance of darbepoetin alfa will be based on dosing records (weekly doses are captured) and categorized as Under Compliant, Compliant, and Over Compliant, and will be defined as follows:             
 
○ Calculated compliance < 80% → Under Compliant
 
○ Calculated compliance ≥ 80% and ≤ 120% → Compliant
 
○ Calculated compliance > 120% → Over Compliant
 
 
 
• Calculated compliance will just be carried to derive compliance category, not provided for any displays. It will be carried using the following formula:             
 
○ Calculated compliance (%) = [(Total # of dosing records with container number) / (Total # of planned dosing)] * 100
 
             where              Total # of planned dosing = [Time on study treatment (days)] / 7              where Time on study treatment (days) = Treatment Stop Date – Treatment Start date + 1           
 
 
When a container number is available in a visit, subjects will receive an injection in the visit (i.e., dosing records may be available even when subjects don't receive injections).
 
 
• For compliance up to Week 4, following formulae will be used:             
 
Total # of actual dosing up to Week 4 = Sum of (Number of dosing records with container number before Week 4 visit)
 
Total # of planned dosing up to Week 4 = [Time on study treatment (days) up to Week 4] / 7
 
• Time on study treatment (days) up to Week 4                = [Week 4 Dosing Date] – [Treatment Start date] + 1 day                If Week 4 dosing date is missing (i.e., withdrawal before Week 4), treatment stop date will be used instead.
 
 
 
• For compliance during the primary efficacy evaluation period, following formulae will be used:             
 
Total # of actual dosing during the EP = Sum of (Number of dosing records with container number on and after Week 40 visit).
 
Total # of planned dosing during the EP = [Time on study treatment (days) during the EP] / 7
 
• Time on study treatment (days) during the EP                = [Treatment Stop Date] – [Week 40 Dosing Date] + 1 day                If Week 40 dosing date is missing (i.e., withdrawal before Week 40), the compliance will not be calculated.
 
 
 

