**Dose Adjustment**

Illustration of dose adjustment algorithm (24-week case)

Visit (Example)	Treatment Start date/ Stop date	Duration	HemoCue Hgb (g/dL)	Dose (mg)	(FL_A)	(FL_B)	(FL_C)
					Adjustment	Over 13 g/dL	Inter-ruption
Day 1	01FEB2017/ 01MAR2017	29	11.1	4	N	N	N
Week 4	02MAR2017/ 15MAR2017	14	11.4	4	N	N	N
Week 8	02APR2017/ 01MAY2017	30	11.8	2	Y	N	N
Week 12	02MAY2017/ 01JUN2017	31	13.4	0	Y	Y	Y
Week 16	02JUN2017/ 01JUL2017	30	12.6	0	N	N	Y
Week 20	02JUL2017/ 01AUG2017	31	11.7	1	Y	N	N
Week 24	-	-	12.3	-	-	N	-

For programmers, note that the flags are for the purposed of illustration, and are not intended to imply any type of requirement.

For summary tables, further details are described within the next items;

- 'Duration (days) of treatment interruption due to Hgb >13.0 g/dL'
- 'Dose adjustment'

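### Per-protocol rule 08 uses different compliance denominators by arm in Weeks 40-52: an undelivered daprodustat supply drops out, while missed darbepoetin injections count

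*SAP*

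**What the plan says.** SAP 15.1.1 lists, as reason 08 for exclusion from the PP population, "Non-compliance with randomized medication (compliance category of under compliant or over compliant") during the primary efficacy evaluation period. SAP 15.6.2 applies the same cut-offs in both arms: below 80% is Under Compliant, 80-120% is Compliant, above 120% is Over Compliant.

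The denominators under those cut-offs differ.

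- **Daprodustat** (SAP 15.6.2, Treatment Compliance of Daprodustat): planned tablets are the "Sum of [(Treatment Stop Date – Treatment Start Date + 1 day) x Planned # of tablet / day in Each Visit". A protocol-driven interruption stays in the sum: "0 mg → 1 tablet/day (i.e., subjects takes placebo tablets"). A visit for which no bottle reached the subject does not: "planned # of tablet/day will be 0 so that the treatment compliance will not be calculated".
- **Darbepoetin alfa** (SAP 15.6.2, Treatment Compliance of Darbepoetin Alfa): "Total # of planned dosing during the EP = [Time on study treatment (days) during the EP] / 7". That time runs from the Week 40 dosing date to the treatment stop date, plus one day. Only dosing records with a container number count as given.

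SAP 6.2 calls for a Week 40 to 52 compliance summary, and rule 08 depends on it. SAP 15.6.2 writes out a formula for that period for darbepoetin but not for daprodustat.

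**The concern.** Rule 08 should treat the same lapse in treatment alike in both arms. As written, a daprodustat interval with no bottle leaves both numerator and denominator, and so do any days between a recorded stop date and the next recorded start date. A darbepoetin week with no injection, inside the span from Week 40 to treatment stop, stays in the denominator as a missed dose.

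PP membership can then depend on arm for the same gap. The PP population is a planned robustness check on non-inferiority: the MMRM, ANCOVA and tipping-point analyses are all repeated in it (SAP 7.1.6). Table 1.27 would also report daprodustat compliance on dispensed time and darbepoetin compliance on calendar time. Within the daprodustat arm the time bases differ as well, because the average daily dose in SAP 15.6.2 divides by time on treatment with interruptions left in.

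**Working it through.** **Plan's own figures.** The documents print no compliance percentage to reproduce. The per-record rule (stop - start + 1) can be checked on the dose-adjustment illustration in SAP 15.6.3. It returns all six printed durations: 29, 14, 30, 31, 30 and 31 days, total 165. The calendar span from 1 February to 1 August 2017 is 182 days. The missing 17 days are 16 March to 1 April, between the record "02MAR2017/ 15MAR2017" and the next start on 2 April. So the record structure can leave days uncounted.

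**Inputs**
- Daprodustat supply: "Daprodustat/placebo will be dispensed once every 4 weeks" (Protocol 7.1, Table 10 notes). One undelivered supply is 28 days.
- Darbepoetin: weekly at the site (Protocol 6.8), giving 12 injections from Week 40 to Week 51.
- Completer's darbepoetin stop date: the Week 52 visit (SAP 15.6.1). On nominal dates the time is 84 + 1 = 85 days, so planned doses are 85/7 = 12.14.
- Case compared: a completer with a four-week gap from Week 44 to Week 48.

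**Daprodustat, no bottle at Week 44, all other tablets taken**
- Planned, at one tablet per day: 28 + 0 + 28 = 56. Taken: 28 + 0 + 28 = 56.
- Compliance: 56/56 = 100%, Compliant. The result is the same at 2, 3 or 4 tablets per day.
- Share of days covered: 56/84 = 66.7%.

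**Darbepoetin, the same four injections missed**
- 8/12.14 = 65.9%, Under Compliant, excluded by rule 08.
- With the ±3-day visit windows at each end, elapsed time is 78 to 90 days. The range is 8/(79/7) = 70.9% to 8/(91/7) = 61.5%, always below 80%.
- Three missed injections also exclude (9/12.14 = 74.1%). Two do not (10/12.14 = 82.4%).
- If a Week 52 injection were counted as given, the four-miss case is 9/12.14 = 74.1%, still excluded.

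**Does another rule catch the daprodustat subject?** Rule 06 requires at least 3 of 4 evaluable Hgb values. Missing only the Week 44 visit leaves 3 in either arm, so rule 06 does not separate the two subjects.

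**One rule for both arms**
- Calendar denominator: daprodustat 56/84 = 66.7% (56/85 = 65.9% on the 85-day span), darbepoetin 65.9%. Both are Under Compliant.
- Dispensed-time denominator: 56/56 and 8/8. Both are 100%.

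The split comes from the denominators alone.

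**The case against.** The strongest reply is that the case is narrow.

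- **Ordinary non-adherence is seen.** A reader might infer that the daprodustat formula misses the largest adherence failures in a self-administered arm. It does not miss bottles delivered but left untaken over a full-length record: 28 untaken days in Weeks 40-52 give 56/84 = 66.7%, Under Compliant. The blind spot is limited to undelivered bottles and gaps between records. This objection stands.
- **Only Weeks 40-52 matter for rule 08.** Over the whole study the same darbepoetin gap gives 48/(365/7) = 92.1%, Compliant. This stands.
- **Darbepoetin has escapes too.** Compliance is not calculated if the Week 40 dosing date is missing. After withdrawal the stop date is the last dose plus 6 days, so trailing missed weeks drop out: 8/(56/7) = 100%. This stands, and it limits the contrast to gaps inside the span.
- **The Compliant label is an inference.** The zero rule could mean that no percentage is produced for the subject at all. The label would then change, but the subject would still have no category on which rule 08 could act.
- **The SAP 15.6.3 illustration proves little.** A reader might take it as 14/31 = 45% adherence scored as 100%. It illustrates dose adjustment, gives no tablet counts and falls between Weeks 4 and 8, outside rule 08. It shows only that records can leave gaps.
- **Gaps are visible elsewhere.** Dose-by-visit tables have a not-administered category, and exposure is listed by subject. That helps a reader of the report but does not change who is in the PP population.
- **Non-delivery may be logistical.** So may a missed injection at the site, and that already counts.

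**Conclusion.** The point holds in limited form. Within Weeks 40-52, PP membership can depend on arm for the same four-week gap: 100% or no category for daprodustat, against 65.9% and exclusion for darbepoetin. This assumes a completer, nominal visit dates, 12 injections, the Week 40 dose given, and the general daprodustat formula applied to records from Week 40 onwards.

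The ITT primary analysis and the mITT principal secondary analysis are untouched. The effect is confined to the PP sensitivity analyses and Table 1.27.

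It is probably small. As an illustration only, with 100 subjects in an arm, one retained subject 2 g/dL low moves the arm mean by 2/100 = 0.02 g/dL, against a margin of 1.0 g/dL. The documents do not say how often bottles go undelivered.

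A reader might infer that the asymmetry favours daprodustat; the documents do not support that. If time off drug lowers Hgb, keeping the daprodustat subject lowers that arm's mean and dropping the darbepoetin subject raises the control mean, and both work against non-inferiority. The direction depends on the subjects affected and is not known in advance.

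**What to change.** Before unblinding, amend SAP 15.6.2 to state a Weeks 40-52 compliance formula for daprodustat. For rule 08, use the same calendar span in both arms, from the Week 40 dose to treatment stop. In that span, count undispensed intervals and days between records at the last prescribed tablets per day instead of zero. State also what category, if any, a subject receives when compliance cannot be calculated.

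The cost is SAP wording and a small programming change using recorded dates and prescribed dose levels. The downside is that some deliveries missed for logistical reasons will count as under-compliance, as missed injections already do for darbepoetin. The PP population may be slightly smaller.
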